- **PET-CT** at present, the low dose or attenuation correction CT portion of a combined PET-CT is not always of optimal diagnostic CT quality for use with Lugano Classification [5]. However, if the site can document that the CT performed as part of a PET-CT is of identical diagnostic quality to a diagnostic CT (with IV and oral contrast), then the CT portion of the PET-CT can be used for measurements and can be used interchangeably with conventional CT in accurately measuring cancer lesions over time. Note, however, that the PET portion of the CT introduces additional data which may bias an investigator if it is not routinely or serially performed.

- **FDG-PET:** While FDG-PET response assessments need additional study, it is sometimes reasonable to incorporate the use of FDG-PET scanning to complement CT scanning in assessment of progression (particularly possible 'new' disease). New lesions on the basis of FDG-PET imaging can be identified according to the following algorithm:
  - Negative FDG-PET at baseline, with a positive FDG-PET at follow-up is a sign of PD based on a new lesion.
  - No FDG-PET at baseline and a positive FDG-PET at follow-up: If the positive FDG-PET at follow-up corresponds to a new site of disease confirmed by CT, this is PD. If the positive FDG-PET at follow-up is not confirmed as a new site of disease on CT, additional follow-up CT scans are needed to determine if there is truly progression occurring at that site (if so, the date of PD will be the date of the initial abnormal FDG-PET scan). If the positive FDG-PET at follow-up corresponds to a pre-existing site of disease on CT that is not progressing on the basis of the anatomic images, this is not PD.
  - FDG-PET may be used to upgrade a response to a CR in a manner similar to a biopsy in cases where a residual radiographic abnormality is thought to represent fibrosis or scarring. The use of FDG-PET in this circumstance should be prospectively described in the protocol and supported by disease-specific medical literature for the indication. However, it must be acknowledged that both approaches may lead to false positive CR due to limitations of FDG-PET and biopsy resolution/sensitivity.

**Note:** A 'positive' FDG-PET scan lesion means one which is FDG avid with an uptake greater than twice that of the surrounding tissue on the attenuation corrected image.

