## APPENDIX C-2: PTCL RESPONSE CRITERIA

Response	Site	CT-Based Response	PET-CT Based Response
Complete Response		Complete radiologic response (all of the following)	Complete metabolic response (even with a persistent mass)
	Lymph nodes and extralymphatic sites	
Target nodes/nodal masses must regress to <math>\leq 1.5</math> cm in longest diameter.
 
No extralymphatic sites of disease.
	
Score <math>\leq 3^*</math> with or without a residual mass on 5-point scale†.
 
It is recognized that in Waldeyer's ring or extranodal sites with high physiologic uptake or with activation within spleen or marrow (e.g., with chemotherapy or myeloid colony-stimulating factors), uptake may be greater than normal mediastinum and/or liver. In this circumstance, complete metabolic response may be inferred if uptake at sites of initial involvement is no greater than surrounding normal tissue even if the tissue has high physiologic uptake.

	Nonmeasured lesion	Absent	Not applicable
	Organ enlargement	Rgress to normal	Not applicable
	New lesions	None	None
	Bone marrow	Normal by morphology; if determinate, IHC negative	No evidence of FDG-avid disease in marrow
Partial Response		Partial remission (all of the following)	Partial metabolic response
	Lymph nodes and extralymphatic sites	
<math>\geq 50\%</math> decrease in SPD of up to 6 target measurable nodes and extranodal sites
 
When a lesion is too small to measure on CT, assign 5 mm X 5 mm as the default value
 
When no longer visible, 0 X 0 mm
 
For a node <math>> 5</math> mm X 5 mm, but smaller than normal, use actual measurement for calculation
	
Score 4 or 5† with reduced uptake compared with baseline and residual mass(es) of any size
 
At interim, these findings suggest responding disease
 
At end of treatment, these findings indicate residual disease

Response	Site	CT-Based Response	PET-CT Based Response
	Nonmeasured lesion	Absent/normal, regressed, but no increase	Not applicable
	Organ enlargement	Spleen must have regressed by > 50% in length beyond normal	Not applicable
	New lesions	None	None

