	New lesions	Regrowth of previously resolved lesions A new node $>$ 1.5 cm in any axis A new extranodal site $<$ 1.0 cm in any axis; if $>$ 1.0 cm in any axis, its presence must be unequivocal and must be attributable to lymphoma Assessable disease of any size unequivocally attributable to lymphoma	New FDG-avid foci consistent with lymphoma rather than another etiology (eg, infection, inflammation). If uncertain regarding etiology of new lesions, biopsy or interval scan may be considered.
	Bone marrow	New or recurrent involvement	New or recurrent FDG-avid foci

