#### Nonmeasured lesions:

Any disease not selected as measured, dominant disease and truly assessable disease should be considered not measured. These sites include any nodes, nodal masses, and extranodal sites not selected as dominant or measurable or that do not meet the requirements for measurability but are still considered abnormal, as well as truly assessable disease, which is any site of suspected disease that would be difficult to follow quantitatively with measurement, including pleural effusions, ascites, bone lesions, leptomeningeal disease, abdominal masses, and other lesions that cannot be confirmed and followed by imaging. In Waldeyer's ring or in extranodal sites (e.g., GI tract, liver, bone marrow), FDG uptake may be greater than in the mediastinum with complete

metabolic response, but should be no higher than surrounding normal physiologic uptake (eg, with marrow activation as a result of chemotherapy or myeloid growth factors).

\*A score of 3 in many patients indicates a good prognosis with standard treatment, especially if at the time of an interim scan. However, in trials involving PET where de-escalation is investigated, it may be preferable to consider a score of 3 as inadequate response (to avoid undertreatment).

†PET 5-point score:

1, no uptake above background; 2, uptake  $\leq$  mediastinum; 3, uptake  $>$  mediastinum but  $\leq$  liver; 4, uptake moderately  $>$  liver; 5, uptake markedly higher than liver and/or new lesions; X, new areas of uptake unlikely to be related to lymphoma.

Abbreviations:

CT, computed tomography; FDG, fluorodeoxyglucose; IHC, immunohistochemistry; LDi, longest transverse diameter of a lesion; MRI, magnetic resonance imaging; PET, positron emission tomography; PPD, cross product of the LDi and perpendicular diameter; SDi, shortest axis perpendicular to the LDi; SPD, sum of the product of the perpendicular diameters for multiple lesions.

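### Appendix C-1 carries its own PET threshold, new-lesion rule and CR upgrade beside the 5-point scale of Appendix C-2, leaving some end-of-treatment CR calls open to two readings

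*Combined protocol and SAP*

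**What the plan says.** Section 11.3.1 sends disease parameters and assessment methods to Appendix C-1 and assigns response by the Lugano criteria in Appendix C-2. Both appendices contain rules for reading PET.

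Appendix C-1 (Methods for Evaluation of Measurable Disease) has three:

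- **Threshold.** A closing Note says a positive lesion "means one which is FDG avid with an uptake greater than twice that of the surrounding tissue on the attenuation corrected image".
- **New lesions.** The algorithm begins: "Negative FDG-PET at baseline, with a positive FDG-PET at follow-up is a sign of PD based on a new lesion". It sets no condition on the cause of the uptake.
- **CR upgrade.** "FDG-PET may be used to upgrade a response to a CR in a manner similar to a biopsy", where a residual abnormality is believed to be scar. No cut-off is given. C-1 adds: "The use of FDG-PET in this circumstance should be prospectively described in the protocol".

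Appendix C-2 works differently. Complete metabolic response is a score of 3 or less "with or without a residual mass on 5-point scale". Score 3 is above mediastinum but not above liver, score 4 is moderately above liver, and score 5 is "uptake markedly higher than liver and/or new lesions". For PET progression by new lesions it requires "New FDG-avid foci consistent with lymphoma rather than another etiology", with infection and inflammation as its examples of other causes. C-2 has site exceptions (Waldeyer's ring, extranodal sites with high physiologic uptake, activated spleen or marrow), a separate marrow rule, and a category X for uptake unlikely to be lymphoma.

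Table 10.0 (notes y and z) schedules CT at Cycle 3 Day 1 and every 2 cycles after that. PET is done at screening and then not until end of treatment or progression.

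**The concern.** One appendix judges a PET lesion against the tissue next to it and the other against mediastinum and liver. Nothing says which cut-off applies when C-1's CR upgrade is used. C-1 asks for that use to be described prospectively, yet no section ties it to the 5-point scale. The Note is the only PET cut-off in C-1, so a reader working from the methods appendix could borrow it for the upgrade.

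The new-lesion rules also differ on cause. Infections are listed toxicities of both drugs (Sections 6.1.1 and 6.1.2), so uptake that is not lymphoma is a realistic finding.

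At stake are the CR rate, a secondary endpoint, and in fewer cases whether and when a patient is recorded as progressing. With at most 18 evaluable patients, a choice of rule made after the scans are seen would be visible in the reported rates.

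**Working it through.** **The plan's own figures.** The point disputes none of them. An exact two-stage binomial calculation and a search over designs (10% versus 30%, one-sided alpha at most 10%, power at least 80%) return the stated optimal design of 0/7 then 3/18. Alpha is 0.0893, power 0.8000, the probability of early stopping at a 10% rate 0.478, and the expected sample size at that rate 12.7. No PET quantity enters this calculation.

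**Comparing the two PET rules.** Let U be lesion uptake, B surrounding-tissue uptake and L liver uptake.

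- C-1 positive: U > 2B.
- C-2 complete metabolic response at an ordinary nodal site (score 3 or less): U ≤ L.

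Write f = B/L. In units of liver uptake the thresholds are 2f and 1, so they coincide only when 2f = 1, that is f = 0.5. The documents give no uptake values, so f is an assumption and is shown over a range:

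| f = B/L (assumed) | Discordant range of U/L | C-1 | C-2 |
|---|---|---|---|
| 0.1 | 0.2 to 1.0 | positive | complete response |
| 0.2 | 0.4 to 1.0 | positive | complete response |
| 0.3 | 0.6 to 1.0 | positive | complete response |
| 0.4 | 0.8 to 1.0 | positive | complete response |
| 0.5 | none | – | – |
| 0.75 | 1.0 to 1.5 | not positive | above score 3 |
| 1.0 | 1.0 to 2.0 | not positive | above score 3 |

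The last two rows take any uptake above liver as exceeding score 3. C-2 describes score 4 only as moderately above liver, so the lower edge of those ranges is approximate.

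**C-2's exceptions do not close the gap.** At the excepted sites C-2 does compare with adjacent normal tissue, but complete response there needs U ≤ B, whereas C-1 is positive only at U > 2B. A focus between 1 and 2 times its surroundings is then neither a complete response in C-2 nor positive in C-1.

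**Effect on the CR rate.** One patient is 1/18 = 5.6 percentage points. For example, 2/18 = 11.1% (95% Clopper-Pearson interval 1.4 to 34.7) against 3/18 = 16.7% (3.6 to 41.4).

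**Effect on progression.** Read at scan level, C-1's first bullet needs a negative baseline PET. That is uncommon here, because eligibility requires disease and Section 2.7 regards PTCL as FDG avid. The second bullet needs no baseline PET, but Table 10.0 schedules one for everyone. The rule matters only if the first bullet is read lesion by lesion: a site negative at screening and positive later. C-1 then gives a sign of progression with no test of cause, while C-2 requires one.

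**The case against.** The strongest reply is that the two rules do different jobs. C-1 uses the word positive only in its new-lesion bullets, positive is not a response category, and the CR-upgrade bullet contains neither the word nor a threshold. Section 11.3.1, note bb of Table 10.0 and the opening line of C-1 all put response under Lugano. C-2 already allows complete metabolic response with a persistent mass, so it can be read as the prospective description that C-1 asks for. The new-lesion bullets rarely apply as written, and C-1 speaks only of a sign of progression, which need not override C-2.

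Most of this stands. A reader who follows Section 11.3.1 strictly would assign the category from C-2, and it would be wrong to say that the Note sets the cut-off for the CR upgrade: that is an inference a reader might draw, not something the text states. What remains is that the upgrade sits in an operative methods appendix with no cut-off, next to a Note that supplies one on a different reference tissue, and no sentence says that C-2 governs it. The difference on the cause of new foci also remains.

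**Conclusion.** The point holds as an inconsistency to be reconciled, with limited reach. The two appendices can describe the same end-of-treatment lesion differently in either direction. That they can follows from the text; how often they do depends on uptake ratios the documents do not give. The main exposure is the CR rate, at 5.6 points per patient in 18. A PET-based new-lesion call that feeds PFS or duration of response is a lesser one.

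A reader might infer that the conflict threatens the primary result, since the verdict turns on 4 responses in 18. The documents do not support that:

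- The synopsis sets ORR after 2 cycles, and that assessment is scheduled by CT.
- Moving a patient from PR to CR leaves ORR unchanged.
- Table 11.3 puts no time limit on achieving CR or PR, so a late PET could in principle turn a CT non-response into a response. That depends on whether the CT or the PET column governs, which is a separate question.
- The chance of exactly 3 or 4 responses in 18, ignoring the stage 1 stop, is 0.105 + 0.168 = 0.27 at a true rate of 30% and 0.230 + 0.215 = 0.45 at 20%. This measures how close the count may fall to the boundary, not how often a PET reading would move it.

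Sample size and error rates are untouched.

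**What to change.** Amend the wording of Appendix C-1:

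1. State that every PET-based response category, including any upgrade of a residual mass to CR, follows the PET-CT column of C-2 with its own exceptions: Waldeyer's ring, extranodal sites with high physiologic uptake, activated spleen or marrow, the marrow rule and category X. A blanket rule that scores 1 to 3 are negative and 4 to 5 positive would override these and should not be used.
2. Delete the Note on twice the surrounding tissue, or confine it expressly to flagging possible new lesions for further assessment.
3. Make a PET-detected new lesion count as progression only under C-2's condition that it is consistent with lymphoma rather than another cause such as infection or inflammation. Keep C-1's CT-confirmation step for foci that CT has not confirmed.

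The cost is small: a few sentences in one appendix, with no added scans, readers or patients.

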## APPENDIX C-2: PTCL RESPONSE CRITERIA

Response	Site	CT-Based Response	PET-CT Based Response
Complete Response		Complete radiologic response (all of the following)	Complete metabolic response (even with a persistent mass)
	Lymph nodes and extralymphatic sites	
Target nodes/nodal masses must regress to <math>\leq 1.5</math> cm in longest diameter.
 
No extralymphatic sites of disease.
	
Score <math>\leq 3^*</math> with or without a residual mass on 5-point scale†.
 
It is recognized that in Waldeyer's ring or extranodal sites with high physiologic uptake or with activation within spleen or marrow (e.g., with chemotherapy or myeloid colony-stimulating factors), uptake may be greater than normal mediastinum and/or liver. In this circumstance, complete metabolic response may be inferred if uptake at sites of initial involvement is no greater than surrounding normal tissue even if the tissue has high physiologic uptake.

	Nonmeasured lesion	Absent	Not applicable
	Organ enlargement	Rgress to normal	Not applicable
	New lesions	None	None
	Bone marrow	Normal by morphology; if determinate, IHC negative	No evidence of FDG-avid disease in marrow
Partial Response		Partial remission (all of the following)	Partial metabolic response
	Lymph nodes and extralymphatic sites	
<math>\geq 50\%</math> decrease in SPD of up to 6 target measurable nodes and extranodal sites
 
When a lesion is too small to measure on CT, assign 5 mm X 5 mm as the default value
 
When no longer visible, 0 X 0 mm
 
For a node <math>> 5</math> mm X 5 mm, but smaller than normal, use actual measurement for calculation
	
Score 4 or 5† with reduced uptake compared with baseline and residual mass(es) of any size
 
At interim, these findings suggest responding disease
 
At end of treatment, these findings indicate residual disease

Response	Site	CT-Based Response	PET-CT Based Response
	Nonmeasured lesion	Absent/normal, regressed, but no increase	Not applicable
	Organ enlargement	Spleen must have regressed by > 50% in length beyond normal	Not applicable
	New lesions	None	None
	Bone marrow	Not applicable	Residual uptake higher than uptake in normal marrow but reduced compared with baseline (diffuse uptake compatible with reactive changes from chemotherapy allowed). If there are persistent focal changes in the marrow in the context of a nodal response, consideration should be given to further evaluation with MRI or biopsy or an interval scan
No response or stable disease		Stable disease	No metabolic response
	Target nodes/nodal masses, extranodal lesions	< 50% decrease from baseline in SPD of up to 6 dominant, measurable nodes and extranodal sites; no criteria for progressive disease are met	Score 4 or 5† with no significant change in FDG uptake from baseline at interim or end of treatment
	Nonmeasured lesion	No increase consistent with progression	Not applicable
	Organ enlargement	No increase consistent with progression	Not applicable
	New lesions	None	None
	Bone marrow	Not applicable	No change from baseline
Progressive disease		Progressive disease requires at least 1 of the following	Progressive metabolic disease
	Individual target nodes/nodal masses	PPD progression:	Score 4 or 5 with an increase in intensity of uptake from baseline and/or
	Extranodal lesions	An individual node/lesion must be abnormal with: Longest diameter (LDi) > 1.5 cm and Increase by ≥ 50% from PPD nadir and	New FDG-avid foci consistent with lymphoma at interim OR • End-of-treatment assessment

Response	Site	CT-Based Response	PET-CT Based Response
		An increase in LD i or smallest diameter (SD i ) from nadir 0.5 cm for lesions $\leq$ 2 cm 1.0 cm for lesions $>$ 2 cm In the setting of splenomegaly, the splenic length must increase by $>$ 50% of the extent of its prior increase beyond baseline (e.g., a 15-cm spleen must increase to 16 cm). If no prior splenomegaly, must increase by at least 2 cm from baseline New or recurrent splenomegaly	
	Nonmeasured lesion	New or clear progression of preexisting nonmeasured lesions	None
	New lesions	Regrowth of previously resolved lesions A new node $>$ 1.5 cm in any axis A new extranodal site $<$ 1.0 cm in any axis; if $>$ 1.0 cm in any axis, its presence must be unequivocal and must be attributable to lymphoma Assessable disease of any size unequivocally attributable to lymphoma	New FDG-avid foci consistent with lymphoma rather than another etiology (eg, infection, inflammation). If uncertain regarding etiology of new lesions, biopsy or interval scan may be considered.
	Bone marrow	New or recurrent involvement	New or recurrent FDG-avid foci

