- r. *Adverse event (AE)* will be assessed using CTCAE v.5.0. SAEs related to study procedures will be recorded and reported from time of informed consent until Day 1 of protocol therapy.
- s. Toxicities AE recording and reporting will continue until the completion of [Safety Follow-up period](#) or until resolution or stabilization of any reportable AE occurring during Safety Follow-up.
- t. *Women of child bearing potential*: Pregnancy serum or urine test.
- u. *Screening laboratory assessments* to be performed within 14 days prior to start of protocol therapy.
- v. *Serum chemistry* panel to include: glucose, Blood Urea Nitrogen (BUN), creatinine, uric acid, total protein, albumin, magnesium, bicarbonate, calcium, inorganic phosphorous, sodium, potassium, chloride, total CO2, total bilirubin, alkaline phosphatase, ALT, AST, and LDH.
- w. *TLS serum chemistry monitoring post-Day 1, Day 2, Day 3, Day 4, Day 5, Day 6, Day 7 and Day 8 dose* to include potassium, uric acid, phosphorus, calcium, and creatinine. **Monitoring times are:** predose, and post dose 6-8 hours

and 24 (+/- 2) hours. Next dose should not be administered until 24 h blood chemistry values are evaluated. See **Table 5.9.1.**

- x. CT/MRI imaging for PTCL at baseline.
- y. *Disease and response assessment:* Cycle 3 Day 1 (-7 days), then every 2 cycles (-7 days). CT scan may take place within 7 days prior to D1 but not after D1 of the cycle in question.
- z. FDG-PET scan will be performed at screening. Subsequent PET scans will not be needed until the EOT visit or disease progression, whichever comes first.
- aa. *Bone marrow biopsy/aspirate* that was performed within 120 days prior to Day 1 may serve as Screening assessment.
- bb. PTCL response (Lugano criteria). Refer to [Section 11.3](#) for details.
- cc. *TLS prophylaxis* to be initiated prior to protocol therapy within 72 hours as stated in [Table 5.9.1](#). Participants should receive continued TLS prophylaxis as clinically indicated.
- dd. Refer to [Section 5.3](#) for the treatment plan. Refer to [Section 6.2](#) for dose modification/ delay guidelines and [Section 5.9](#) for supportive care guidelines.
- ee. Romidepsin will be administered intravenously on Days 1, 8, and 15 of each cycle. A window is allowed for romidepsin infusion visits (within  $\pm 3$  days of day 1 and within +3 days of days 8 and 15)
- ff. *Pill Diary* will be given to the participant and will be reviewed for adherence. See [Appendix G](#).

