**Table 11.3. Clinical Endpoints**

Endpoint	Patients	Definition
Overall response rate (ORR)	Evaluable patients	Proportion of patients achieving CR or PR
Complete response (CR) rate	Evaluable patients	Proportion of patients achieving CR
Time to response	Evaluable patients	Date of initiation of protocol treatment to date when criteria for response (PR or CR) is first met
Duration of response (DOR)	CR and PR only	Date when criteria for response (CR or PR) is first met until date criteria for PD or relapse is first met
Progression free survival (PFS)	Evaluable patients	Date of initiation of protocol treatment to date criteria for PD is first met or death as a result of any cause
Overall survival (OS)	Evaluable patients	Date of initiation of protocol treatment to date of death from any cause

**Note:** Evaluable patients are patients evaluable for response, as defined in [Section 12.3](#).

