### **Methods for Evaluation of Measurable Disease**

All measurements should be taken and recorded in metric notation using a ruler or calipers. All baseline evaluations should be performed as closely as possible to the beginning of treatment and never more than 4 weeks before the beginning of the treatment.

The same method of assessment and the same technique should be used to characterize each identified and reported lesion at baseline and during follow-up. Imaging-based evaluation is preferred to evaluation by clinical examination unless the lesion(s) being followed cannot be imaged but are assessable by clinical exam.

- Clinical lesions

Clinical lesions will only be considered measurable when they are superficial (e.g., skin nodules and palpable lymph nodes) and  $\geq 10$  mm ( $\geq 1$  cm) diameter as assessed using calipers (e.g., skin nodules). In the case of skin lesions, documentation by color photography, including a ruler to estimate the size of the lesion, is recommended.

- Conventional CT and MRI

This guideline has defined measurability of lesions on CT scan based on the assumption that CT slice thickness is 5 mm (0.5 cm) or less. If CT scans have slice thickness greater than 5 mm (0.5 cm), the minimum size for a measurable lesion should be twice the slice thickness. MRI is also acceptable in certain situations (e.g. for body scans).

Use of MRI remains a complex issue. MRI has excellent contrast, spatial, and temporal resolution; however, there are many image acquisition variables involved in MRI, which greatly impact image quality, lesion conspicuity, and measurement. Furthermore, the availability of MRI is variable globally. As with CT, if an MRI is performed, the technical specifications of the scanning sequences used should be optimized for the evaluation of the type and site of disease. Furthermore, as with CT, the modality used at follow-up should be the same as was used at baseline and the lesions should be measured/assessed on the same pulse sequence. It is beyond the scope of the Lugano Classification [5] to prescribe specific MRI pulse sequence parameters for all scanners, body parts, and diseases. For this trial, MRI will not be used as standard imaging study for disease assessment.

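### Appendix C-2: the two size branches for a new extranodal site on CT appear transposed, so small nonspecific findings can be scored as progression

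*Combined protocol and SAP*

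**What the plan says.** Response is assessed by the Lugano classification, which Appendix C-2 sets out in a table (Section 11.3.1, reference 50). In the CT column, "Progressive disease requires at least 1 of the following". The new-lesions cell of that block contains these rules:

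- Nodes: "A new node $>$ 1.5 cm in any axis".
- Extranodal sites: "A new extranodal site $<$ 1.0 cm in any axis; if $>$ 1.0 cm in any axis", followed by the condition "its presence must be unequivocal and must be attributable to lymphoma".
- Any other disease: "Assessable disease of any size unequivocally attributable to lymphoma".

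The CT rows for CR, PR and stable disease each say only *None* under new lesions, with no size limit or qualifier.

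On imaging, CT response assessment falls at Cycle 3 Day 1 and then every 2 cycles. For PET, Table 10.0 (note z) says: "Subsequent PET scans will not be needed until the EOT visit or disease progression, whichever comes first".

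Progression feeds three things:

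- PFS, defined in Table 11.3 as "Date of initiation of protocol treatment to date criteria for PD is first met or death as a result of any cause".
- Duration of response, which ends at progression or relapse (Table 11.3).
- Removal from protocol therapy (Section 5.6).

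**The concern.** As printed, the smaller and less certain finding meets the looser standard, and the larger finding meets the stricter one. A tiny new spot of unknown cause would be progression on its own, while a clearly larger new site would first need proof of what it is.

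The cell is an operative endpoint rule. A site that follows it literally could date progression too early on a nonspecific small finding, which shortens PFS and duration of response and ends treatment. It could also date progression too late when a new site above 1.0 cm is not yet judged unequivocal, which lengthens both. If some readers follow the cell and others follow the cited classification, the same scan could be scored differently.

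**Working it through.** **1. The extranodal line against its neighbours**

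| Rule (Appendix C-2, CT, progression) | Small finding | Larger finding |
|---|---|---|
| New node | 1.5 cm or less: does not meet the node rule | above 1.5 cm: progression |
| New extranodal site, as printed | below 1.0 cm: progression, no condition | above 1.0 cm: only if unequivocal and due to lymphoma |
| Assessable disease of any size | only if unequivocally lymphoma | only if unequivocally lymphoma |

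- The node rule asks for more size before calling progression. The extranodal line asks for less.
- The any-size line requires certainty whatever the size. An unconditional branch below 1.0 cm makes that requirement empty for small extranodal sites.
- A pre-existing lesion needs a longest diameter above 1.5 cm plus defined growth. A lesion growing from 1.4 to 1.5 cm therefore fails that criterion, while a new 4 mm extranodal spot is progression as printed.
- The PET column of the same row requires new foci to be consistent with lymphoma and allows biopsy or an interval scan if the cause is uncertain. The CT branch below 1.0 cm has no such safeguard.
- Appendix C-1 treats small size as a limit on reliability. For CT slices thicker than 5 mm, "the minimum size for a measurable lesion should be twice the slice thickness".

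**2. Exactly 1.0 cm.** The extranodal line uses strict inequalities on both sides, so neither branch contains 1.0 cm. Such a lesion is still progression under the any-size line if it is unequivocally lymphoma. The gap lies in that line, not in the whole cell.

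**3. Which column governs.** Because PET is not required between screening and end of treatment or progression, scheduled on-treatment calls rest on the CT column.

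**4. Does it reach ORR?** CR and PR on CT require no new lesions.

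- Read literally, any new site of any size rules out CR or PR at that assessment, whichever way the signs in the progression row point.
- If *None* means no new lesion as the progression row defines it, the printed signs can change a CR or PR at that assessment.
- The documents do not say which reading applies.

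**5. The design, and what would follow under the second reading.** Section 12.1.2 gives these inputs: 7 patients in stage 1, stop at 0 responses; 18 in total, reject the null at 4 or more; rates 10% and 30%.

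P(reject | p) = Σ from x = 1 to 7 of C(7,x) p^x (1−p)^(7−x) × P(Bin(11,p) ≥ 4 − x)

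- p = 0.10: 0.0893, within the stated 10%. Early stop: 0.9^7 = 0.478.
- p = 0.30: 0.800, the stated power. Early stop: 0.7^7 = 0.082.

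The plan's figures are reproduced. Now assume that a fraction f of true responders is scored as progression. The values of f are illustrative and none comes from the documents.

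| f (assumed) | Effective ORR | Power |
|---|---|---|
| 0 | 0.300 | 0.800 |
| 5% | 0.30 × 0.95 = 0.285 | 0.762 |
| 10% | 0.30 × 0.90 = 0.270 | 0.720 |
| 20% | 0.30 × 0.80 = 0.240 | 0.621 |

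Power starts at 0.800 with no slack, so any positive f takes it below 80%. The table shows sensitivity and does not estimate an effect.

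**The case against.** The strongest reply is that the governing standard is the Lugano classification, which the protocol names repeatedly. Assessors who know it may never apply a misprint in a transcribed table. That lowers the likely frequency but does not remove the risk, because the appendix is what a site has in hand.

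A second reply is that the signs may have been misread from the PDF. Two signs would have to be misread in mirror fashion while neighbouring ones read sensibly. That is unlikely, but the original page should be checked.

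Three stronger inferences are tempting, and the documents do not support them:

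- *Each false progression costs one response of 18 (1/18 = 5.6 points of ORR) and the trial loses power.* The bare *None* in the CR and PR rows may already exclude the patient at that assessment. A CR or PR already achieved still counts in ORR. No misclassification rate is given.
- *A 1.0 cm lesion is not covered at all.* The any-size line catches it when it is unequivocally lymphoma.
- *Large genuine lesions will be missed.* A large, clear lymphoma lesion would normally meet the condition. What remains is possible delay for those not yet judged unequivocal.

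**Conclusion.** The inconsistency stands on the printed text, without recourse to the cited source: the two branches of the extranodal line contradict both neighbouring rules in their own cell and appear transposed. Taken literally, the line can produce false progression from small nonspecific findings, with early PFS and duration-of-response dates and removal from therapy. It can also delay the dating of some true progressions above 1.0 cm. The two errors pull PFS and duration of response in opposite directions, so the net bias has no known sign.

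The size cannot be estimated, because the documents give neither the frequency of new small extranodal findings nor how assessors would read the cell. An effect on ORR is conditional on reading *None* through the progression definition. No design figure changes: 0 of 7, then 4 or more of 18, alpha 0.0893 and power 0.800 all stand. The conclusion assumes that the signs in the original page match the text reviewed.

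**What to change.** 1. Check the two inequality signs on the original page of Appendix C-2.
2. If they are as read here, reconcile the two branches of the extranodal line with the node rule and the any-size rule in the same cell, and with the Lugano classification in reference 50. The rule also triggers removal from therapy, so the wording should come from that reconciliation. It should not be settled by this review.
3. State which branch includes exactly 1.0 cm.
4. Align *None* under new lesions in the CR, PR and stable-disease rows with the reconciled definition, so that no patient is left unclassified.
5. Re-check any progression already called on a new extranodal site, and correct PFS and duration-of-response dates where needed.

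The cost is one line and three short entries in one table, plus a limited re-read of affected scans. Sample size, error rates and the decision rule stay as they are.
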